Educating providers about smoking counseling has been shown to increase their engagement with patients regarding smoking cessation.⁷ One intervention, educational outreach visits, or academic detailing, have been shown to have a small but consistent effect on physician prescribing behaviors.⁸ We hope to use a multi-modality educational intervention, including academic detailing, to enhance the effects of the EMR tools and increase use of smoking cessation resources.

[figure not shown]
By incorporating decision support tools, facilitating use of the Quit Line, and educating clinicians about counseling and pharmacotherapy, we hope to improve the use of these services and increase engagement between clinicians and patients about smoking cessation and to ultimately decrease smoking across the health system

4. Study Procedures

a. Study design, including the sequence and timing of study procedures (distinguish research procedures from those that are part of routine care).

Overview: We propose a cluster randomized trial to test the effectiveness of an Epic-based BPA with and without supplemental education and academic detailing on 1) Quit Line referrals, 2) Patient Quit Line engagement, 3) Prescription of pharmacotherapy, and 4) Smoking cessation. To this end, we will randomize the 35 sites from Johns Hopkins Community Physicians to one of three arms: 1) Cluster C: no intervention initially, BPA added after 6 months; 2) Cluster B: BPA alone with emailed link to MD Quit Line educational material; 3) Cluster A: BPA with online educational modules, a quick-reference educational document, and additional academic detailing. Outcomes will be assessed at 6 and 12 months.

Conceptual Model:

Study design: This will be a **waitlist-control, cluster randomized trial**. JHCP sites will be randomized to Arm A (BPA plus educational interventions), Arm B (BPA only), or Arm C (control group, no intervention). After 6 months, Cluster C will be granted access to the BPA.

Study Population: The study will include all JHCP practices and primary care providers at those sites. JHCP is the largest health specialty group practice in Maryland and cares for over 230,000 patients at 22 practice sites throughout Maryland and Washington, DC. There are approximately 190 adult primary care providers at these sites. Patients will be at least 18 years of age and will be active smokers as indicated in the EMR.

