Based on prior research with a comparable tool used in the inpatient setting where compared to control arm physicians, intervention physicians were more likely to order tobacco treatment medication (24% v. 9%, P = 0.0001, Fisher's exact test), and make a referral to the state smokers' quitline (19% v. 0%, P < 0.0001, we expect a 20% absolute increase in the percentage of the population of active smokers who are referred to the Quit Line among providers that receive the BPA, and a 30% increase among providers receiving the BPA + educational materials/detailing, compared to the control condition. Our main outcome, is quitline referral, which is a dichotomous outcome. We will use logistic regression accounting for clustering by site and provider to determine the difference in quit-line referral between the BPA only arm, and the waitlist control (B vs C), the BPA + education and the waitlist control (A vs C), and the BPA + educational materials arm and the BPA only arm (A vs B). The two primary testing contrasts will be B vs C and A vs C, each will be evaluated at type I error of 0.025 to safeguard the overall type I error for testing the 2 primary contrasts. The secondary contrast of A vs B is exploratory in nature, to estimate the potential incremental increase in quitline referral with additional provider education. The difference in % referral between arms and its corresponding 95% CI will be calculated. Due to the design of cluster randomization by sites, provider level and patient level characteristics that are not balanced by randomization between arms will be adjusted for in the logistic regression model.

In this 3-arm trial, we expect 7 JHCP sites per arm, with an average cluster size of 1000 smokers per site (based on current patient numbers in the clinics, number of smokers, and proportion willing to quit). Assuming intracluster correlation of 0.1, and a 5% quitline referral in the control Arm C, we will have 88.6% power to detect a 20% absolute increase in quitline referral in Arm B when testing the contrast of B vs C using a Z-test at type I error of 0.025, and 99.4% power to detect a 30% absolute increase in quitline referral in Arm A when testing the contrast of A vs C using a Z-test at type I error of 0.025.

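### With about 7 randomised sites per arm, the power uses a Z-test and the clustered logistic analysis names no small-sample reference; read against z, it would not hold 0.025 per contrast

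*Combined protocol and SAP*

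**What the plan says.** All the analysis detail is in section 7c.

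- Size: "we expect 7 JHCP sites per arm, with an average cluster size of 1000 smokers per site", with an assumed intracluster correlation (ICC) of 0.1 and 5% referral in Arm C.
- Primary analysis: "We will use logistic regression accounting for clustering by site and provider". The contrasts B vs C and A vs C are primary, and "each will be evaluated at type I error of 0.025 to safeguard the overall type I error for testing the 2 primary contrasts".
- Covariates: "provider level and patient level characteristics that are not balanced by randomization between arms will be adjusted for in the logistic regression model".
- Estimate: "The difference in % referral between arms and its corresponding 95% CI will be calculated".
- Power: "88.6% power to detect a 20% absolute increase in quitline referral in Arm B", computed for an increase "in Arm B when testing the contrast of B vs C using a Z-test at type I error of 0.025"; and 99.4% for a 30-point increase in Arm A, from the same kind of test at 0.025.

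Section 4a makes the site the unit of randomisation, stratified by size. The documents do not say whether the model uses random effects or estimating equations. They name no variance estimator, degrees of freedom, small-sample correction or permutation test.

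The site count is inconsistent. The abstract and the Study Population paragraph of 4a give 22 sites, while the Overview of 4a randomises 35. Seven per arm fits 22.

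**The concern.** Each primary contrast compares about 7 sites with 7. However many smokers each site contributes, the between-site variance has to be estimated from about 14 sites (or 21 if all three arms are pooled). A normal reference ignores that uncertainty. Maximum likelihood and uncorrected robust estimators also tend to understate the variance when clusters are few.

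Two things are at stake. The first is the split of alpha into 0.025 per contrast, which is there to protect the overall error and would not do so if a clustered logistic model were read against z. The second is the power statement, which describes a known-variance test that the trial cannot carry out.

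**Working it through.** **Inputs from the documents.** 7 sites per arm, 1000 smokers per site, ICC 0.1, 5% in Arm C, 25% in B, 35% in A, alpha 0.025 per contrast. Sidedness is not stated; two-sided reproduces the plan's figures (one-sided gives 91.8 to 93.0% for B vs C), so the critical z is 2.2414.

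**1. Reproduce the stated power.**
- Design effect = 1 + 999 × 0.1 = 100.9. Effective n = 7000 / 100.9 = 69.4 per arm.
- B vs C: SE = √[(0.05×0.95 + 0.25×0.75)/69.4] = 0.0582; 0.20/0.0582 = 3.436; Φ(3.436 − 2.241) = 88.4% (stated 88.6%).
- A vs C: SE = √[(0.05×0.95 + 0.35×0.65)/69.4] = 0.0630; 0.30/0.0630 = 4.765; power 99.4% (stated 99.4%).

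**2. Same calculation with a t reference (noncentral t, same noncentrality).**

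| Reference | Critical value | B vs C | A vs C |
|---|---|---|---|
| z | 2.241 | 88.4% | 99.4% |
| t, 18 df (21 sites − 3 arms) | 2.445 | 82.9% | 98.5% |
| t, 12 df (7 + 7 − 2) | 2.560 | 79.6% | 97.7% |

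**3. True size of a nominal 0.025 contrast read against z.** Under a normal site-level model with 21 sites:
- REML-type variance (divisor 18): P(|t18| > 2.2414) = 3.8%.
- Maximum-likelihood variance (divisor 21): P(|t18| > 2.2414 × √(18/21)) = P(|t18| > 2.075) = 5.3%.
- At least one false positive over the two contrasts, which share Arm C: 4.6% with known variance, 6.8% with REML and z, 9.3% with ML and z.

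**4. Simulation of the logistic model.** Random intercepts for site and provider, fitted by maximum likelihood, 21 sites with 9 providers each ("There are approximately 190 adult primary care providers at these sites"; 190/22 ≈ 9). The provider variance is an assumption (for example SD 0.5 on the logit scale).
- One set, with common null rates of 5, 15 and 25%, gave a size of 5.0 to 5.4% with z and at least one false positive in 8.7 to 9.5%. On the same fits, t with 18 df gave 3.2 to 4.1% and t with 12 df gave 2.6 to 3.4%.
- A separate Laplace fit gave about 4.2% with z and at least one false positive in 7.3 to 7.9%. A simple site-level version of the ML analysis also ran low on those draws (4.8 to 5.1%, against 5.3 to 5.4% in the long run).

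**5. Logistic regression with only an uncorrected robust standard error, read against z.** At null rates of 5 / 15 / 25% and ICC 0.1, size is 10.8 / 6.9 / 6.3% with beta-distributed sites and 11.5 / 7.5 / 6.6% with logit-normal sites. With beta sites and ICC 0.02 it is 6.8 / 6.1 / 6.1%.

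**6. Site count.** The t calculation of step 2 for B vs C gives 79.6% (7 v 7), 81.4% (8 sites in C) or 84.6% (8 sites in B) if 22 sites are randomised, and 96.7 to 97.7% if 35 are. With 35 sites, ML variance read against z still has a size of about 4.0%.

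**The case against.** The plan ties the Z-test to the power calculation alone and never says the logistic model will be read against z. That stands. A reader might infer that each contrast will run at about 5% and the family at about 9%. The documents do not support this as a flat statement, because it needs both maximum-likelihood variance and a Wald z reference, and the plan commits to neither. With an unbiased variance the figures are 3.8% and 6.8%. Nor does a site-mean z-test, which can sit close to nominal, mark the lower end of what the plan allows, since it is not a logistic analysis.

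A reader might also infer that the power arithmetic is wrong or that the trial is underpowered. Neither follows. The arithmetic reproduces, and in the first set of simulations in step 4 the planned type of model had 94.0 to 96.2% power for B vs C even against t with 12 df. Those figures depend on assumed variance components, but size is the main issue.

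Finally, it can be said that replacing the primary analysis with an unadjusted site-level t-test would discard the planned covariate adjustment. That is correct, and the gap does not require it: a small-sample reference for the planned model closes most of it.

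What the objection does not remove is that nothing in the plan requires anything better than z, and every clustered logistic method examined above exceeds 0.025 when read against z.

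**Conclusion.** The concern holds as a gap in specification with a measurable consequence. Read against z with 7 sites per arm, a nominal 0.025 contrast has a size of about 3.8 to 5.3% with random intercepts, and about 6 to 11% with an uncorrected robust standard error. The family-wise error is about 7 to 9% with random intercepts, against 5% intended. The random-intercept range rests on a normal site-level model; the robust figures depend on the null rate, the ICC and the distribution of sites. Covariate adjustment was not simulated.

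The stated powers are right for a known-variance Z-test. On the plan's own difference in proportions they become 79.6% and 97.7% with 12 df, or 82.9% and 98.5% with 18 df. The 35 versus 22 site conflict is a separate inconsistency, but it decides which degrees of freedom and which power apply. This should be fixed.

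**What to change.** 1. Before outcomes by arm are analysed, keep the logistic model as primary and complete its specification. For example: *The primary model is a logistic regression with random intercepts for site and provider. Each primary contrast is tested at two-sided 0.025 against a t distribution with k1 + k2 − 2 degrees of freedom, where k1 and k2 are the numbers of sites in the two arms (12 for 7 + 7).* In simulation 12 df brought the maximum-likelihood fit close to nominal (2.6 to 3.4%). With an REML-type variance it would be slightly conservative: P(|t18| > 2.560) = 2.0%.
2. Report as a supporting check either a site-level log-odds t-test or a permutation test that re-randomises within the size strata. Give the difference in percentage referred a t-based interval (2.179/1.960 = 1.11, so 11% wider than z on 12 df), and state that the named test decides.
3. Restate both powers with the t reference: about 80% and 98% on the plan's own calculation, or about 87% and 98% for a site log-odds t-test on 12 df with beta-distributed sites.
4. Reconcile 35 sites with 22 sites and 7 per arm, and compute the power for the reconciled number.

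No extra sites or data are needed. The price is a somewhat lower stated power for B vs C. Timing matters, because section 4a already describes the academic detailing in the past tense, so this version postdates some delivery. If outcomes by arm have already been analysed, report the small-sample result as a labelled post hoc sensitivity analysis.
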